10.6.1.3. Assessment of the Severity of Adverse Events

The severity (toxicity grade) of AEs will be graded according to the NCI CTCAE, Version 4.03 (see Appendix 1).

10.6.1.4. Assessment of the Causal Relationship of Adverse Events to Study Drug

The investigator will assess causal relationship between study drug and each Adverse Event and classify each AE as either related or unrelated. In determining if an AE is study drug related, the Investigator shall take into account the following question: "Is there a reasonable possibility that the event may have been caused by the study drug?" Investigators shall use their knowledge of the patient, the circumstances surrounding the event, and an evaluation of any potential alternative causes to determine whether or not an adverse event is considered to be related or unrelated to study drug. The following guidance shall be taken into consideration when determining causality:

- Temporal relationship of event onset to the initiation of study drug
- Course of the event, considering especially the effects of dose reduction, discontinuation of study drug, or reintroduction of study drug (as applicable)
- Known association of the event with the study drug or with similar treatments
- Known association of the event with the disease under study
- Presence of risk factors in the patient or use of concomitant medications known to increase the occurrence of the event
- Presence of non-treatment-related factors that are known to be associated with the occurrence of the event

The following terms for assessment of the causality to study drug or study procedures are to be used:

- Unrelated: There is not a temporal relationship to study drug administration (eg, too early, too late, or study drug not taken), or there is a reasonable causal relationship between another drug, concurrent disease, or circumstance and the AE.
- **Related**: There is a reasonable causal relationship between the study drug and the AE. The event responds to withdrawal of study drug, and recurs with re-challenge, when clinically feasible.

For patients receiving combination therapy, causality will be assessed individually for each study drug.

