6.1.1.1. G1T38 Dose Evaluation Criteria

In the first Cohort of 6 patients, a relatively low dose of G1T38 will be administered to allow for a sufficient safety window. This low dose of G1T38 is anticipated to be below the maximum tolerated dose (MTD), even if osimertinib increases the systemic exposure of G1T38 (see Section 4.4.2). However, if ≥ 2 of 6 patients experience a DLT, then the MTD will have been exceeded and a lower G1T38 dose level may be explored. If 1 or fewer patient(s) in the first cohort of 6 experience a DLT, then 3 patients may be enrolled at the next SMC recommended G1T38 dose level.

The G1T38 dose evaluation criteria for Cohorts 2 and beyond are listed below.

- If there is no DLT in a given dose level cohort, then 3 patients may be enrolled at the next SMC recommended G1T38 dose level.
- If there is 1 DLT in a given dose level cohort of 3 patients, an additional 3 patients will be enrolled at this G1T38 dose level. If no additional DLTs are observed (ie, ≤ 1 out of 6 with DLT), escalation may proceed to the next SMC recommended G1T38 dose level.
- If there are \geq 2 DLTs in a given dose level cohort, then the MTD will have been exceeded and a lower G1T38 dose level may be explored as determined by the SMC.

6.1.1.2. Definition of Dose-Limiting Toxicities (Applicable to Cycle 1 Day -16 through Cycle 1 Day 28 in Part 1)

Dose-limiting toxicities are drug-related AEs defined as follows:

- Grade 4 neutropenia
- \geq Grade 3 neutropenic infection/febrile neutropenia
- Grade 4 thrombocytopenia
- ≥ Grade 3 thrombocytopenia with bleeding
- \(\geq \) Grade 3 nonhematologic toxicity (additional criteria for nausea, vomiting, diarrhea, or fatigue: lasting > 5 days with maximal medical management)

• Liver function test abnormalities meeting Hy's Law criteria (aspartate aminotransferase [AST] or alanine aminotransferase [ALT] ≥ 3 × upper limit of normal [ULN] and total bilirubin ≥ 2 × ULN). All study drugs must be permanently discontinued in any patient meeting Hy's Law criteria.

Each patient will be evaluated for toxicity during the Treatment Phase. The toxicity of G1T38 administered with osimertinib will be assessed by the investigators using National Cancer Institute (NCI) CTCAE, Version 4.03.

6.1.2. Part 2

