8.3.3. Dose Modification

8 3 3 1 G1T38

Dose adjustments of G1T38 for toxicities are to be made according to the organ system showing the greatest degree of drug-related toxicity. Toxicities will be graded using NCI CTCAE, Version 4.03. No more than 2 G1T38 dose level reductions in total are allowed for any patient. Toxicity that requires dose level reduction more than twice will lead to permanent discontinuation of G1T38 dosing for the individual patient.

Since fatigue can be a symptom of cancer progression, dose reduction will only be performed if the fatigue is deemed to be drug related in the opinion of the investigator.

An off-drug period of up to 21 consecutive days is permitted to allow recovery from any toxicity. Off-drug periods of greater than 21 days may be allowed if the investigator believes the potential benefits of continued treatment outweigh the potential risks, but such cases must be discussed with the medical monitor.

Dose Modifications for G1T38-Related Hematologic Toxicity

The G1T38 dose level adjustments in Table 8-1 are based on hematologic adverse reactions, except lymphopenia (unless associated with clinical events, eg, opportunistic infections).

Table 8-1 G1T38 Dose Level Adjustments Based on G1T38-related Hematologic Toxicities

CTCAE Grade of Hematologic Toxicity	G1T38 Dose Adjustment
Grade 3	Continue G1T38 and repeat CBC at next scheduled visit.
≥ Grade 3 neutropenia associated with a documented infection or fever ≥ 38.5°C ≥ Grade 3 thrombocytopenia associated with bleeding	Withhold G1T38 and monitor counts weekly until ANC \geq 1 x 10 ⁹ /L. Resume therapy at the next lower dose. Withhold G1T38 and monitor counts weekly until platelet count \geq 75 x 10 ⁹ /L. Resume therapy at the next lower dose.
Grade 4	Withhold G1T38 and monitor counts weekly until ANC \geq 1 x 10 ⁹ /L and platelet count \geq 75 x 10 ⁹ /L. Resume therapy at the next lower dose.

ANC = absolute neutrophil count; CBC = complete blood count; CTCAE = Common Terminology Criteria for Adverse Events

Granulocyte-colony stimulating factor

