 - Disease progression can be considered as a worsening of a patient's condition attributable to the disease for which the investigational product is being studied. It may be an increase in the severity of the disease under study and/or increases in the symptoms of the disease. The development of new, or progression of existing metastasis to the primary cancer under study should be considered as disease progression and not an AE
- Hospitalization due to signs and symptoms of disease progression

An unexpected AE is any AE that is not identified in nature, severity, or frequency in the current IB or product information. The sponsor or designee shall be responsible for determining expectedness; this is not the responsibility of the investigator.

• An Adverse Drug Reaction (ADR) is defined as an AE that is caused by a drug (aka drug-related AE). An unexpected ADR is an adverse reaction, the nature or severity of which is not consistent with the applicable product information (eg, IB for an unapproved investigational medicinal product). All noxious and unintended responses to a medicinal product related to any dose should be considered ADRs. The phrase "responses to a medicinal product" means that a causal relationship between a medicinal product and an AE is at least a reasonable possibility, ie, the relationship cannot be ruled out. All serious and unexpected ADRs will have expedited reporting to the regulatory agencies following the ICH requirements

It is the responsibility of the investigator to document all AEs that occur during the study and every effort should be made to adequately capture all possible AEs. Patients should be encouraged to report AEs spontaneously or in response to general, nondirected questioning. Adverse events should be reported on the appropriate page of the eCRF.

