
- Relative study day for the onset of AE: (AE onset date – date of first dose + 1) if AE onset date is on or after the date of first dose; otherwise (AE onset date – date of first dose)
- Relative study day for the end of AE: (AE stop date – date of first dose + 1) if AE stop date is on or after the date of first dose; otherwise (AE stop date – date of first dose)
- The duration of AE: AE stop date – AE onset date + 1

Drug related AEs are defined as related if causality is related.

Every attempt will be made to obtain complete information for AEs regarding severity (i.e., CTCAE Grade) and relationship to drug; however, in the rare case of missing data, the following conservative approach will be taken for summary purpose. The non-imputed raw data will be presented in AE listings,

- Missing AE grade will be classified as ‘Grade 3’
- Missing AE relationship will be classified as “Related”

G1 Therapeutics, Inc.
Clinical Study Protocol G1T38-03
Statistical Analysis Plan

AEs related to hematological toxicity is of significant clinical interest, Certain PTs will be consolidated into larger categories outside the traditional MedDRA coding guidance. [Table 6-1](#) outlines those terms that will be consolidated.

Table 6-1 Hematologic Preferred Terms to be Consolidated

Presented SOC/PTs in the table	Dictionary SOC/PT
Blood and lymphatic system disorders / Neutropenia	Blood and lymphatic system disorders / Neutropenia
	Investigations / Neutrophil count decreased
Blood and lymphatic system disorders / Anemia	Blood and lymphatic system disorders / Anemia
	Blood and lymphatic system disorders / Anaemia
	Investigations / Red blood cell count decreased
	Investigations / Hemoglobin decreased
Blood and lymphatic system disorders / Thrombocytopenia	Blood and lymphatic system disorders / Thrombocytopenia
	Investigations / Platelet count decreased
Blood and lymphatic system disorders / Lymphocytopenia	Blood and lymphatic system disorders / Lymphocytopenia
	Blood and lymphatic system disorders / Lymphopenia
	Investigations / Lymphocyte count decreased
Blood and lymphatic system disorders / Leukopenia	Blood and lymphatic system disorders / Leukopenia
	Investigations / White blood cell count decreased

In addition, the following gastrointestinal PTs are collapsed in [Table 6-2](#).

Table 6-2 Gastrointestinal Preferred Terms to be Consolidated

Presented term in the table	Preferred Term
Stomatitis	Mouth ulcers
	Mouth ulceration
	Mucosal inflammation
	Stomatitis

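### The definition of 'Related' adds a withdrawal and re-challenge test that is narrower than the protocol's other causality standards, so some DLTs and related AEs could be recorded as Unrelated

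*Protocol*

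**What the plan says.** Protocol 10.6.1.4 has the investigator classify each AE as related or unrelated, separately for each study drug. The guiding question is "Is there a reasonable possibility that the event may have been caused by the study drug". Six considerations follow. One is the course of the event, including the effect of reducing, stopping or reintroducing the drug, where that applies.

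The two categories are then defined. 'Related' opens with "There is a reasonable causal relationship between the study drug and the AE" and continues: "The event responds to withdrawal of study drug, and recurs with re-challenge, when clinically feasible". 'Unrelated' has positive criteria of its own: no temporal relationship to dosing, or a reasonable causal relationship with another drug, disease or circumstance.

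Protocol 10.6.1.1 uses a broader standard for adverse drug reactions, namely that "a causal relationship between a medicinal product and an AE is at least a reasonable possibility, ie, the relationship cannot be ruled out".

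The recorded category matters later on. Protocol 6.1.1.2 states "Dose-limiting toxicities are drug-related AEs defined as follows", and SAP 4.2.2 repeats this. SAP 4.2.1 states "Drug related AEs are defined as related if causality is related", and SAP 5.2.10 builds a long series of related-TEAE tables on that flag.

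**The concern.** Response to withdrawal and recurrence on re-challenge are useful supporting evidence. Here they are also written into the definition of the category to be ticked, on a scale with no 'possibly related' level. One field is therefore governed by three standards: the guiding question, the definition, and the adverse drug reaction wording in 10.6.1.1. The definition is the narrowest. Investigators who follow it closely and investigators who follow the guiding question could code the same event differently.

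The possible error has a direction. A stricter test for 'Related' can only move events out of that category, so it can lower the DLT count that drives escalation in 6.1.1.1 and thin out the related-TEAE tables. SAP 4.2.1 treats a missing relationship as Related, but that rule does not touch an event actively recorded as Unrelated.

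**Working it through.** **Step 1. Test types of event against the added sentence.** The feasibility qualifier can be read as covering re-challenge only (narrow) or both limbs (broad).

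| Event | Narrow reading | Broad reading |
|---|---|---|
| Drug stopped, event does not improve | Fails | Fails: withdrawal was feasible, with no response |
| Event resolves, drug restarted, no recurrence | Fails | Fails |
| Event resolves, restart barred by the protocol | Excused | Excused |
| Fatal event | Can fail the withdrawal limb | Excused |
| Drug continued through the event | Withdrawal limb untested | Open: depends on what counts as feasible |

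The first two rows do not depend on how the qualifier is read. The fatal case does.

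**Step 2. Check the second row against the protocol's own example.** Protocol 4.3.1 reports a Grade 4 neutropenia in Study G1T38-02, counted as a DLT. It recovered with interruption, and after restart at a lower dose there was no further Grade 4 episode. Read literally, an event with that course would not satisfy the recurrence limb. Two limits apply. A lower-dose restart is arguably not a full re-challenge, and the Table 4-1 footnote shows that G1T38-02 used a graded scale (possibly, probably or definitely related). The example shows that recurrence is a poor test here. It does not show how this protocol's definition was applied.

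**Step 3. Check which haematologic events can affect the DLT count.** For Grade 3 events Table 8-1 says "Continue G1T38 and repeat CBC at next scheduled visit". Uncomplicated Grade 3 cytopenias are not DLTs under 6.1.1.2. The haematologic DLTs are Grade 4 neutropenia or thrombocytopenia, neutropenic infection or febrile neutropenia of Grade 3 or higher, and thrombocytopenia of Grade 3 or higher with bleeding. Table 8-1 withholds G1T38 for such toxicities, so response to withdrawal can usually be observed. For uncomplicated Grade 3 cytopenias only the related-AE tables could be affected.

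**Step 4. Ask where an event that fails 'Related' goes.** A temporally plausible event with no other cause does not meet 'Unrelated' either. The definitions leave a gap, and the binary field makes the investigator choose a side.

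**Step 5. Illustrate the sensitivity of escalation.** The plan states no figure to reproduce. Let p be the true DLT rate and m the share of true DLTs recorded as Unrelated. Neither is given in the documents; both are assumptions. The observed rate is q = p(1 − m). From the rules in 6.1.1.1:

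- Cohort 1 passes with at most 1 of 6: (1 − q)^6 + 6q(1 − q)^5
- A 3+3 cohort clears with 0 of 3, or 1 of 3 then 0 of 3: (1 − q)^3 + 3q(1 − q)^2 × (1 − q)^3

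With p = 0.30:

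| m | q | Cohort 1 passes | 3+3 cohort clears |
|---|---|---|---|
| 0 | 0.30 | 0.420 | 0.494 |
| 0.10 | 0.27 | 0.487 | 0.557 |
| 0.20 | 0.24 | 0.558 | 0.622 |
| 0.30 | 0.21 | 0.631 | 0.687 |

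For m from 0 to 0.25, Cohort 1 moves from 0.655 to 0.776 at p = 0.20 and from 0.109 to 0.274 at p = 0.50. The 3+3 figures move from 0.709 to 0.814 and from 0.172 to 0.351. Miscoding from any cause would give the same numbers. Because the mechanism reaches only some DLTs, m is the share of DLTs exposed to it times the share of those miscoded, and may be close to zero.

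**The case against.** The strongest reply is that the section, read as a whole, does not make withdrawal and re-challenge a gate. The guiding question is broad, and withdrawal and reintroduction are one consideration of six. Protocol 10.6.1.11 wants causality stated at the initial report, when the outcome of stopping or restarting is often unknown. The qualifier can excuse an impossible re-challenge, so toxicities for which restart is barred, such as ILD or Hy's Law cases, are not excluded on that ground. A sensible investigator may never apply the sentence strictly. All of this stands, and it is why the size of the effect cannot be stated. It does not remove the conflict, because the definition is what the investigator consults when ticking the box.

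The safeguards also stand. SAEs within the reporting period are reported whatever their causality (10.6.1.9), and deaths not clearly due to progression are reported as SAEs (10.6.1.2). The SMC reviews all safety data (6.1.1). The SAP tabulates all TEAEs, Grade 3 or higher TEAEs, serious TEAEs and TEAEs leading to death without regard to relatedness. These limit the harm, but the escalation rule itself counts DLTs.

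A reader might infer that every fatal, irreversible or treated-through toxicity is excluded from 'Related'. The documents do not support that: the qualifier may exempt fatal events, and treated-through events are not clearly excluded. A reader might also infer that an event failing 'Related' automatically becomes Unrelated. It does not, because 'Unrelated' has its own criteria.

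**Conclusion.** The wording conflict is real and worth correcting. The added sentence makes 'Related' narrower than the question in the same section and than the standard in 10.6.1.1, and the scope of its qualifier is unclear. On a literal reading, events that do not improve after stopping, or do not recur on restart, can fail 'Related'. Fatal events may fail, depending on the reading.

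The possible error runs toward fewer DLTs and fewer related TEAEs, in Part 1 only, since the SAP records that Part 2 will not be conducted. Its size is unknown. It would be tempting to conclude that DLT rates are biased down and escalation biased up. The documents do not show that: they give neither a true DLT rate nor a miscoding rate, and zero miscoding is possible. The escalation figures show only how sensitive the rules would be if miscoding occurred.

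**What to change.** In Protocol 10.6.1.4:

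- Delete the withdrawal and re-challenge sentence from the definition of 'Related'. The list of considerations already covers the point as supporting evidence.
- Define 'Related' as a reasonable possibility that the study drug caused the event, consistent with 10.6.1.1.
- Reword 'Unrelated' as no such reasonable possibility. If only 'Related' were changed, an event with a plausible alternative cause could meet both definitions. With both changed, the categories are exclusive and exhaustive.

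For Part 1 data already collected, review Grade 3 or higher events in the DLT window (Cycle 1 Day -16 through Cycle 1 Day 28) that were coded Unrelated to both drugs against this standard before database lock. Document the review and any changes.

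The cost is a short wording change in the protocol and eCRF guidance, plus a limited review of events. Somewhat more AEs may be classed as related.

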10.6.1.5. Assessment of the Outcome of Adverse Events

The outcome will be assessed according to the following:

- Fatal
- Not recovered/not resolved
- Recovered/resolved with sequelae
- Recovering/resolving
- Recovered/resolved

Unknown

10.6.1.6. Method, Frequency, and Time Period for Detecting Adverse Events and Serious Adverse Events

Adverse events and SAEs are reported following the first dose of study drug through 30 days after last dose of study drug (ie, the Post-Treatment Visit).

10.6.1.7. Documentation of Adverse Events and Serious Adverse Events

All AEs will be documented in the appropriate section of the eCRF. The CTCAE, Version 4.03 grading scale referenced in Appendix 1 is provided to assist in categorizing and grading AEs. All SAEs (see Section 10.6.1.2) will be additionally documented on the SAE report form.

10.6.1.8. Adverse Event Coding

Adverse event verbatim terms provided by the investigator will be coded by G1 Therapeutics or its designee using the latest version of the MedDRA as specified in the statistical analysis plan (SAP).

10.6.1.9. Reporting of Serious Adverse Events

The reporting period for SAEs begins from the time of first dose of study drug through and including 30 calendar days after the last administration of G1T38. Any SAE that is thought to be related to the study drug and that occurs after the reporting period must be reported **within 24 hours** of discovery of the SAE PPD Pharmacovigilance. SAEs that occur prior to the first dose of study drug that are a direct result of a study-related procedure shall additionally be reported as an SAE to PPD Pharmacovigilance.

SAE information will be collected on the eCRFs, therefore it is imperative that any SAE be entered onto the electronic SAE Form within 24 hours of learning of the event. If the EDC system is not operational, the paper SAE Form must be completed within 24 hours and faxed to the number below.

PPD Pharmacovigilance:

North America

24 hour Safety [contact] hour Safety [contact]

EMEA/APAC

24 hour Safety [contact] hour Safety [contact]

10.6.1.10. Follow-up of Adverse Events

All AEs (both serious and nonserious) will be followed up in accordance with good medical practice until resolution, return to baseline, or it is deemed that further recovery is unlikely. All measures required for AE management and the ultimate outcome of the AE will be recorded in the source document and reported to the sponsor.

All unresolved AEs should be followed by the investigator until the events are resolved, the patient is lost to follow-up, or the AE is otherwise explained, or further recovery is not deemed to be feasible. At the last scheduled visit, the investigator should instruct each patient to report any subsequent event(s) that the patient, or the patient's personal physician, believes might reasonably be related to participation in this study.

Prior to the conclusion of the study at the site, the investigator should notify the medical monitor of any SAE occurring at any time after a patient has discontinued or terminated study participation that may reasonably be related to the study drug. While the study is ongoing, all deaths should be reported via the electronic data capture system regardless of relationship to study drug, even if the patient has discontinued participation in the study.

After study conclusion, the investigator should notify the sponsor of any death or SAE they are aware of occurring at any time after a patient has discontinued or terminated study participation that may reasonably be related to the study drug. The sponsor should also be notified if the investigator should become aware of the development of cancer or of a congenital anomaly in a subsequently conceived offspring of a patient that has participated in this study.

10.6.1.11. Regulatory Aspects of Adverse Event Reporting

The sponsor or its representative will report the following suspected unexpected serious adverse reactions (SUSARs) to the independent ethics committee (IEC)/institutional review board (IRB) in an expedited time frame:

• SUSARs that have arisen in the current clinical study that was assessed by the IEC/IRB

The sponsor or its representative will report all SUSARs to the Competent Authority, the Medicine Evaluation Board, and the Competent Authorities in other Member States, if applicable in an expedited time frame.

SUSARs that are already reported to the European Medicines Agency Eudravigilance database do not have to be reported again to the Competent Authority and the Medicine Evaluation Board because they have direct access to the Eudravigilance database.

The expedited reporting will occur no later than 15 calendar days after the sponsor has first knowledge of the adverse reactions. For fatal or life-threatening cases the term will be a maximum of 7 calendar days for a preliminary report with another 8 days for completion of the final report. The investigator is encouraged to discuss with the medical monitor any adverse experiences for which the issue of reportability is unclear or questioned.

It is important that the investigator provide his/her assessment of relationship to study drug at the time of the initial report.

